7.2.4 Obtaining informed consent: Nominated consultee consent

Where a patient lacks capacity to consent and a personal consultee is not contactable 12 hours following screening for eligibility, then a nominated consultee will be identified to advise the research team. The nominated consultee will usually be the patient's treating Trauma and Orthopaedic surgeon, but may also be another healthcare professional, such as an orthogeriatrician. If that surgeon (or healthcare professional) is a member of the research team, another independent healthcare professional will be identified.

7.2.5 Obtaining informed consent: Retrospective patient or personal consultee consent

For participants initially unable to consent, but who subsequently regain capacity to consent during their ward stay, an appropriate member of the research team will provide study information and ample opportunity to ask questions and discuss the study with their family and carers. They will then be asked to provide written or verbal consent for continuation in the study. If the participant does

not wish to continue the study, they can choose to decline continued participation either partly (to the intervention and or follow up data collection) or fully including hospital data collections.

For participants unable to consent prior to surgery, and required a nominated consultee, but who do not subsequently regain capacity to consent, every effort will be made to contact a personal consultee to advise the research team about the patient's continued participation in the study and gain retrospective personal consultee consent. See appendix 1 for study flow chart; Appendix 2 for "Patients with capacity" and Appendix 3 for "Patients lacking capacity".

8. DESCRIPTION OF STUDY INTERVENTION, COMPARATORS AND STUDY PROCEDURES

8.1 Description of comparator

We will ask senior nursing staff to collect data on the frequency of mouth care per patient in their unit over a single day, once per month before the intervention starts, including at the lead site. Senior nursing staff will be asked to observe practice and complete standardised forms.

8.2 Mouth care intervention

In participating units, for each recruited patient we will ask nursing staff to complete an oral health assessment tool once just after recruitment. We will provide laminated posters which can be displayed above the participant's bed.

Each recruited participant will be given a mouth care pack at recruitment, consisting of a bag containing a bottle of alcohol free Chlorhexidine 0.2% , a 10ml tube of lip moisturiser and a small headed soft toothbrush, contained within a bag branded with the study logo. We will ask staff to store the bag on the bedside cabinet as a reminder. This pack can be taken with the patient on discharge or at transfer to other care settings.

After recruitment participants will be offered mouth care three times daily and we will ask staff to document each of these episodes on a simple daily recording sheet, provided as part of the study. Participants will be encouraged to take part in as much of their mouth care as possible, and staff will be trained in dementia-friendly techniques (e.g. hand over hand techniques) using the training videos described above. Healthcare assistants will assist the patient where necessary (ranging from verbal prompting to physical assistance) to undertake the mouth care intervention (see Table 2) three times per day, before/after meals. Patients with delirium and dementia may be shown a short video on iPad explaining what will happen. If the intervention is declined, a more limited intervention will be offered (e.g. lip moisturiser only), and the intervention will be offered again at the next round.

Mouth care will be recorded on a daily recording sheet either by staff or patient, documenting whether the intervention was delivered, any issues, and how much help was needed.

Table 2: Mouth care intervention

Dentition	Action
Teeth	
 • Put on the appropriate PPE • Provide the mouth care kit • Dip soft toothbrush in chlorhexidine mouthwash, squeeze once • Brush teeth, gums and tongue, 2 minutes using clock in bay • Apply lip moisturiser
Dentures	
 • Put on the appropriate PPE • Provide labelled denture pot • Remove dentures, safely transfer to pot and rinse in water under tap • Dip toothbrush in the chlorhexidine mouthwash and clean dentures. Dab off the excess. • Brush gums and tongue, and any natural teeth for 2 minutes using bay clock • Reinsert clean dentures into mouth • Apply lip moisturiser • Bedtime only: Advice to remove dentures into labelled denture pot with water.

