11.3 Foreseeable AEs & SAEs

All related AEs should be reported using the study AE reporting forms within 48 hours of the Investigator becoming aware of the event. As the study treatment procedures investigated forms part of basic personal hygiene for participants, we will not be collecting unrelated AEs or SAEs. An SAE form may be triggered following the initial AE form as applicable. This is a low risk study, and potential related adverse events would include:

Expected AEs include:

- Confrontational behaviour around mouth care and towards staff (participants with Dementia)
- Staining on teeth as a result of Chlorhexidine use (e.g. consuming tea straight after intervention)
- Gum bleeding
- Minor accidental injury to mouth while brushing
- Tooth loss
- Broken dentures or loss of dentures
- Spillage of mouthwash resulting in slips and falls
- COVID infection risk to staff and patients as similar to all inpatients

Unexpected AEs include:

- Aspiration of mouthwash
- Drinking mouthwash
- Allergic reaction to lip moisturiser

Training in delivering oral interventions to patients with delirium/dementia will be delivered by our speech and language team, who have a wealth of experience in this area. Confrontational behaviour is common in this population and the ward teams are generally experienced in dealing with patients with delirium or dementia, as it forms a part of 'normal business'. Not opening the mouth will be taken as lack of consent to proceed with the intervention.

Mouth care is not classed as an aerosol generating procedure and standard ward PPE, as per each sites individual hospital guidelines, will be worn. This could include, gloves, plastic apron, fluid repellent surgical face mask and visor (see, Section 14.1).

SAEs/AEs that are foreseeable, or expected, in the treatment of hip fractures/medical procedures do not need to be reported and only variables on the CRF and/or Patient Questionnaires will be collected including HAP episodes.

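### Section 8.2 keeps the chlorhexidine bottle at every participant's bedside, with no exception for delirium, dementia or lack of capacity, although section 11.3 foresees drinking of the mouthwash

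*Protocol*

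**What the plan says.** Under section 8.2 every recruited participant receives a pack, described as "consisting of a bag containing a bottle of alcohol free Chlorhexidine 0.2" (per cent), with a lip moisturiser and a soft toothbrush. The storage request follows: "We will ask staff to store the bag on the bedside cabinet as a reminder". It carries no condition. A second bedside prompt is available: "We will provide laminated posters which can be displayed above the" participant's bed.

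Table 2 sets out what happens at a round. For natural teeth the steps include "Provide the mouth care kit", dipping the brush in the mouthwash and squeezing it once. For dentures the row has "Dip toothbrush in the chlorhexidine mouthwash and clean dentures", after which the excess is dabbed off.

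Section 11.3 introduces its event lists with the words "potential related adverse events would include". The Unexpected sub-list contains "Aspiration of mouthwash" and "Drinking mouthwash". The same section says that the speech and language team will train staff in delivering oral care to patients with delirium or dementia.

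Section 15.6 gives dental discolouration as the only risk to patients. Under sections 6.3.1, 6.3.2 and 8.2 the pack goes with the patient on a COVID move, a transfer or a discharge.

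**The concern.** The study summary (section 1) says that the work concentrates on patients with delirium and dementia. Some of them may not understand what is in the bottle. Section 8.2 places the bottle next to them all day, and section 11.3 shows that the authors foresaw that mouthwash might be drunk. The protocol therefore names a hazard and also fixes a storage arrangement that leaves the product within reach. Nothing in the text connects the two.

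At stake is participant safety in this study, and the storage practice that a definitive trial would inherit from it. No estimate, sample size or analysis is affected.

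**Working it through.** The point rests on no statistical figure, so the check is mainly a comparison of sections. A short calculation gives scale.

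**Step 1: what is fixed.** Section 8.2 makes one storage request for all participants, and the bottle is in the bag. This is a stated instruction, not a detail left open for another document.

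**Step 2: what is foreseen.** Section 11.3 names drinking and aspiration of mouthwash as potential related events but does not say how they would arise. Aspiration can equally happen during brushing, so it adds little to an argument about storage. Drinking can also happen during a round, but it is the event that access between rounds would make possible. The point therefore rests on drinking.

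**Step 3: which safeguards are described, and when they act.**

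| Safeguard | Section | When it acts |
|---|---|---|
| Help from healthcare assistants | 8.2 | During a round |
| Dip and squeeze once; dab off excess | Table 2 | During a round |
| Short video for patients with delirium or dementia | 8.2 | Before or at a round |
| Speech and language team training on delivering care | 11.3 | During a round |
| Closed mouth treated as refusal | 11.3 | During a round |
| Related AE form within 48 hours of awareness | 11.3 | After an event |
| Serious, related and unexpected event: central team within 24 hours, REC within 15 working days | 11.2 | After an event |
| Safety reporting to 90 days | 11 | After an event |
| Oversight committee review of safety | 14.5 | After an event |

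No row acts on access to the bottle between rounds.

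**Step 4: does the pack carry a storage rule when it moves?** Section 6.3.1 sends products and instructions with a COVID-positive patient, but the content of those instructions is not given. Section 6.3.2 sends the pack on transfer or discharge for use up to 4 weeks and states no storage rule. Recording of daily mouth care stops on the new ward. Reporting of related adverse events does not.

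**Step 5: scale.** The protocol's own total comes first, from Table 1:

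- Site 1: 56 + 4 × 112 = 504
- Site 2: 56 + 3 × 112 = 392
- Site 3: 56 + 2 × 112 = 280
- Site 4: 45 + 90 = 135
- Total: 504 + 392 + 280 + 135 = 1311

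The unit-months are 15 + 12 + 9 + 6 = 42, and 1311 / 42 = 31.2. Both figures agree with section 5.2.

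Section 12.3 puts the share of hip fracture patients who lack capacity at 30-40% and plans on 40% needing a consultee:

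- 0.30 × 1311 = 393
- 0.40 × 1311 = 524

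This applies a hip fracture share to all recruits, some of whom are medical patients. Section 7.2.5 also expects some participants to regain capacity on the ward. The range approximates how many would enter through a consultee.

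**The case against.** **Controls may exist outside this text.** Staff are trained (8.2.1), the speech and language team trains for this very subgroup (11.3), and wards have their own storage policies. Section 8.2 is only a request, so nothing stops staff from moving a bottle for one patient. This stands as a limit: it cannot be said that no control exists. But the only storage instruction given is to keep the bag at the bedside, and training that follows the protocol would repeat it. Section 11 also writes another product hazard, pink foam swabs, into the protocol itself.

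**The response to an event is sound.** A reader might infer that the events are under-reported or wrongly classed as unexpected. The document does not support that. The Unexpected label puts a serious related case on the faster route to the central team and the REC. Reporting also continues after transfer. These measures detect events but do not prevent them, which is why the storage point remains.

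**The risk is ungraded.** The mouthwash is alcohol free and the study is described as low risk. This stands, and it caps the weight of the point.

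**Section 15.6 is a short summary.** It also leaves out gum bleeding, mouth injury, tooth loss and slips, all listed in 11.3. That is correct. Adding ingestion would not make the list complete, but it would record the risk that the storage rule addresses.

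**The study can correct itself.** A staff focus group (7.1), weekly huddles (8.2.2) and ward observation (10.2) can all prompt changes. They would work after a problem is noticed, and a line in 8.2 works beforehand.

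**Consistency and workload.** Section 3 wants an intervention that is simple and the same for all patients, and it names time and product availability as barriers. Two storage arrangements do add a step. The care in Table 2 stays identical, however, and section 3 also asks for a design that suits patients with dementia and delirium first.

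**Conclusion.** The point holds as a low-cost safety precaution. Section 8.2 asks for bedside storage of the bottle for everyone, section 11.3 foresees mouthwash being drunk, and nothing in the protocol limits access between rounds for participants who may not understand what the product is.

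Its size cannot be given. The document has no event rate, bottle volume or severity. A reader might take the 393 to 524 as the number in danger, but it is only an approximate count of people needing a consultee, not of people able or likely to drink the mouthwash. A reader might also infer that the study exposes participants to a demonstrated or uncontrolled harm. The document shows neither, and a control may sit in training material or ward policy.

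The conclusion assumes that no such unseen control already overrides the bedside request. If one does, the remaining task is to bring 8.2 into line with it.

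**What to change.** In section 8.2, keep the branded bag at the bedside as the reminder, with the poster where one is used. Then add a rule to this effect: for participants who lack capacity, have delirium or dementia, or are judged by ward staff to be at risk of drinking the mouthwash, the bottle is kept out of unsupervised reach and staff bring it to each round. The arrangement is reviewed if capacity changes. Other participants keep the bottle in the bag.

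Put the same line into the existing staff training and into the instructions that travel with the pack under 6.3.1 and 6.3.2. Add ingestion of mouthwash to the patient risks in 15.6. Repeating the rule in Table 2 is optional. Section 11.3 should stay as it is, because its classification serves reporting.

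The cost is a few sentences and one training line. No outcome, sample size or analysis changes. The downside is a slightly longer set-up at each of the three daily rounds for these participants. That could modestly lower delivery in the consultee subgroup, which has its own progression criterion in Table 4 (green above 60%). The size of that effect is unknown, so the results should be read with it in mind.

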8.2.1 Staff training

Staff will be trained in general oral hygiene care by the Mouth Care Matters team, with a specific section on the study intervention delivery.

These sessions will be delivered face to face if possible or socially distant training via online meetings or video/s.

Staff members will be signed off as competent to deliver the intervention by the study team or mouth care champions using a training log. Staff are not required to have GCP or on the study delegation log to provide the mouth care intervention or to fill in the mouth care assessment documentation from wards due to the nature of the study and the number of staff involved at each cluster

8.2.2 Staff involvement in mouth care delivery

Mouth care champions will be identified at the start of the study for each participating site. The mouth care champion will usually be a healthcare assistant, ideally with an interest in mouth care. The mouth care champion will be asked to conduct weekly huddles with participating nursing staff to discuss and resolve problems, promote the intervention and to act as a bridge to the study team to feedback concerns and ideas.

Mouth care champions will feed back comments to the study team via electronic systems and or with qualitative research team via weekly phone calls. Research nurses will log any significant

comments from the staff delivering the intervention via the study log. This will be fed back to the study team, which can then be shared with other sites if appropriate.

The Study Log, along with the training videos will be used to contribute to a final practical tool, at the end of the study, for other sites interested to deliver a similar intervention. The tool might take the form of videos or might also include written information, which can be uploaded to the Mouth Care Matters website.

8.2.3 Fidelity of the intervention

The fidelity of the intervention will be assessed using a number of methods, including the documentation of mouth care and feedback recorded on the study log from mouth care champions/other healthcare staff during weekly huddles. The qualitative research team will undertake observation exercises and also interview staff and patients about the delivery of the intervention. As a further quality measure, unannounced plaque scoring will be undertaken by a dental trainee, using modified Quigley Hein scores (25) on five patients per site who have received mouth care in the preceding 24 hours, after the first three months of transition.

8.3 Definition of end of study

The study will end when the final site has undertaken the final follow-up for the final patient and all data queries have been resolved. Analysis of data will then occur.

9. PUBLIC AND PATIENT INVOLVEMENT (PPI)

The study proposal has been developed with PPI at all stages since identifying the research question. We have engaged with patients, carers, clinicians, Nurses, Health care assistants and wider stakeholders at various levels to ensure the research proposal answers the key feasibility questions for this patient group, especially those with dementia and delirium.

We conducted a focus group meeting at the lead applicant's site with former patients who had received treatment for hip fractures, and their family members at the outline stage. A patient advisory group (PAG), consisting of up to eight members led by our PPI co-applicant will continue to be involved during the conduct of this study and supported by the study team member/s.

The PAG will meet at regular intervals throughout the setup phase, the study phase and the dissemination stages of the study, and will be supported by the core study team.

At the end of the study, the PAG will help develop a lay summary of trial results and assist in the public dissemination plans, as appropriate, based on the study findings.

We will keep a narrative log over the lifetime of the study detailing the interaction and involvement between our PPI members, and the study. Our PAG members will have access to guidance regarding getting involved in research from the NIHR PPI team in the North East and North Cumbria and INVOLVE. Project manager will support them throughout the study duration as PPI lead.

10. DATA COLLECTION

10.1 Quantitative data collection

10.1.1 Baseline assessments

The study will collect baseline data on all recruited participants prior to them starting the mouth care intervention. This will include oral health assessment data, EQ5D-5L and demographic data. The participant will be asked to complete two EQ5D-5L assessments, one based on how they were one week prior to hospital admission and a second based on how the participant is at the time the data is being collected.

10.1.2 Demographic, health economic and HAP data collection

During the study we will collect prospective data on all antibiotic prescriptions on all four wards via daily visits by a research nurse. Methods of retrieving antibiotic data across the different wards will be explored. Antibiotic data will be retrieved electronically where possible or prospectively via screening drug cards. For cases of HAP, indication not recorded and source unknown, antibiotic prescriptions may be correlated with clinical notes, and routinely collected clinical, biochemical and radiological data.

EQ-5D-5L data will be collected from all patients, by use of proxy where the patient is unable, at 90 days after discharge. The use of EQ-5D-5L patient reported outcome measures (PROMs) data to provide baseline values will also be investigated (10.1.1). Health care resource utilisation within secondary care will be estimated using the outcome measures listed in Table 3.

Table 3: Data collection for quantitative analysis

Type	Variable	Source	Population	Point of data collection
Recruitment	Number approached Number eligible Number consented Type of consent	Research Nurse/Clinician	All ward patients	At screening / consent
Patient covariates*	Age Sex Diagnosis 4AT Score Rockwood Clinical Frailty Scale	Clinical notes	All recruited participants	At study entry
Primary outcome	Proportion of delivered mouthcare episodes of eligible mouth care episodes, per unit, per month	Mouth care documentation	All recruited Participants	Monthly
Secondary outcomes	Proportion of: Patient refusal Staff related non delivery of intervention Time to maximal mouth care delivery	Mouth care documentation	All recruited participants	Monthly
Staff training	Proportion staff trained in mouth care per unit	Off duty log and research logs	All nurses and health care assistants per unit	Monthly
Efficacy of mouth care intervention	Modified Quigley Hein Plaque Scores	Prospective (by Study team)	A sample of Five patients per site during intervention phase having received minimum twice daily mouth care in preceding 24 hours	Random
Infection outcomes	Antibiotic prescriptions	Prospective (Research Nurse)	All recruited participants	Daily while on ward
HAP outcome data	HAP episodes Have they had a CXR? Y/N Was there a diagnosis of HAP? Obs- highest NEWS on day starting abx WCC/CRP on day starting abx	Clinical notes Webice Vitalpac (or equivalent in each site)	Subset of patients with HAP	Daily while on ward

	Oxygen level/sats on day starting abx			
Other outcome data	Length of stay- acute hospital Death in hospital Death within 30 days EQ-5D at 90 days	Hospital records, contact with participant or consultee	All recruited participants	Once
Discharges/transfers	Discharge Transfer destination Discharge date	Hospital records, contact with participant or consultee	All recruited participants	Once

10.2 Qualitative data collection

Researchers from the York Trials Unit will conduct a qualitative interview study with key stakeholders to address important issues in the delivery of the intervention. We would expect these interviews to be short and focused on the following feasibility issues:

- Ward staff (including senior nurses, nurses and health care assistants (n=16-20, at least 2 per site until saturation is reached) will be asked about experience of delivering and documenting (or managing/supervising) the oral care intervention, understanding of the intervention, adequacy of training, confidence in performing intervention, impact on workload, potential for sustainability and any safety concerns.
- Senior hospital nursing staff (n=4, at least 2 per trust), will be asked about sustainability and workload implications for staff.
- Patients/family members (n=16-20), including patients with dementia/delirium, will be asked about the acceptability of the components, the utility of the video and frequency of the intervention.

We will briefly observe each ward on up to three occasions to gain insight into how the oral intervention is delivered in practice. We will avoid imposing structure on our observations, rather writing detailed field notes immediately after the observation period. As 'outsiders', our intention is to question practices and assumptions that are taken for granted. Through observation, supplemented by informal conversations we will examine the:

- Nature of interactions (how the content of service delivery used and adapted to individual needs, in particular with those patients with dementia/delirium)
- Physical environment (where the oral care intervention delivery takes place; how the physical environment constrains/promotes the delivery of good quality care.

These observations will be used to refine the intervention and training iteratively, and to customise training videos accordingly.

